8.3.1 Pragmatic cluster RCT

Analyses will follow CONSORT guidelines and intention-to-treat principles, including all participants as randomized. A flowchart will describe the inclusion and follow-up of participants by study arm.

Baseline characteristics will be described by study arm with summary statistics such as median and interquartile range or number and percentage; no formal testing between arms will be performed. Outcomes will be described by arm using summary statistics. The two primary outcomes, the proportion of children with a severe complication and the proportion of children appropriately hospitalized, will be assessed using a random effects logistic regression models with the cluster included as a random effect. Results will be reported with odds ratios, risk differences and 95% confidence intervals (CI). Binary secondary outcomes will be evaluated in the same way. Continuous secondary outcomes will be assessed using random effects linear regression models, reporting adjusted mean differences between arms with 95% CIs.

All models will be adjusted for randomization stratification factors and any baseline variables found to be randomly imbalanced across arms. Assessment for imbalances between baseline variables will be by visual inspection only; there will be no formal testing of baseline characteristics across randomized groups.^{53,54}

For the analysis of the primary endpoints, we will use a hierarchical fallback procedure, which is a closed test procedure using a weighted Bonferroni.^{55,56} This method recycles unspent significant levels to test subsequent hypotheses with a pre-specified hypothesis sequence.⁵⁷ This uses alpha propagation making it more powerful than the Bonferroni method.

The primary outcomes will be evaluated according to hierarchy of importance as follows:

H_1 : There is no difference between the experimental arm and control arm with respect to severe complications by day 7

H_2 : There is no difference between the experimental arm and control arm with respect to hospital admissions within 1 day of the primary consultation

First, we would test the null hypothesis H_{12} which is that neither H_1 nor H_2 are significant. We would reject the null hypothesis of H_{12} if either $p_1 \leq \alpha_1$ or $p_2 \leq \alpha_2$ where α is equally distributed between the endpoints i.e. $\alpha_1 = 0.025$ and $\alpha_2 = 0.025$.

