3.3 Blinding

This is an open-label study.

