5.5 Baseline Participant Characteristics

Socio-demographic data of children enrolled and their caregivers will be summarised. Additional characteristics of interest, such as danger signs and symptoms as reported by the caregiver, will be presented as part of baseline summaries. Baseline data will be presented by intervention arm using median and associated interquartile range (IQR) if continuous and as counts and percentages if categorical. Summary statistics will be of non-missing values, with the number (%) of missing values given if data are not complete. Assessment will be made for baseline imbalances between the randomisation groups by visual inspection only and no formal testing will be performed.

For the baseline summaries, age of children will be reported as a continuous variable in months but also disaggregated in age groups. In the database, the age is estimated based on recommended standardised age disaggregation groups [6] with a different level of accuracy depending on the information provided by the caregiver. Based on age estimates, children are further categorised into young infants (<60 days) and children 60days-59 months. More details are provided in Appendix A.

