6.2 Analysis Methods

6.2.1 Analytical Methods

Outcomes will be described by arm using summary statistics. In particular, counts and percentages will be used for binary variables and reported with one decimal place; mean and standard deviation (SD) or median (IQR) for continuous variables depending on their distribution. Mean and median will be displayed with one decimal place and SD and IQR will be presented with two decimal places.

The two primary outcomes will be assessed using a random effects logistic regression model with the cluster included as a random effect. If convergence issues arise due to sparse data, clusters may be dropped or combined to higher grouping level (e.g. district).

Results will be reported with odds ratios, risk differences and their associated 95% confidence intervals (CI). The control arm will be used as reference category.

Secondary outcomes and other binary outcomes of interest will be evaluated in the same way.

Other continuous outcomes of interest will be assessed using random effects linear regression model with the cluster included as a random effect. Results will be reported in terms of adjusted mean differences between arms with associated 95% CIs.

Modelling of secondary outcomes will be performed if numbers allow.

For interim analyses and DMC analyses, only the two primary outcomes will be presented. Modelling will not be performed and results will be reported in terms of summary statistics only.

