6.2.2 Adjustment for Covariates

All models will be adjusted for stratification factors (facility type, location) and baseline variables that are found to be randomly imbalanced across arms. As described in Section 5.5, the imbalance will only be assessed visually and without performing any formal comparison.

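### Covariates for both co-primary models are chosen by eye from by-arm baseline tables, so the primary model is data-dependent and cannot be reproduced from the SAP

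*SAP*

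**What the plan says.** SAP 6.2.1 sets the primary model: "The two primary outcomes will be assessed using a random effects logistic regression model with the cluster included as a random effect". SAP 6.2.2 then covers adjustment for all models. It names facility type and location as stratification factors and adds "baseline variables that are found to be randomly imbalanced across arms", with the qualification that "the imbalance will only be assessed visually and without performing any formal comparison".

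SAP 5.5 describes the tables on which that judgement is made. They are split by arm and hold child and caregiver characteristics, including danger signs and symptoms reported by the caregiver. It repeats the method: "Assessment will be made for baseline imbalances between the randomisation groups by visual inspection only and no formal testing will be performed". Protocol 8.3.1 carries the same rule, adjusting for the stratification factors and "any baseline variables found to be randomly imbalanced across arms".

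On blinding, SAP 3.3 says "This is an open-label study". Protocol 7.2 blinds the research assistant who collects outcomes by phone. Neither document says whether the person choosing covariates is blind to arm or to outcomes.

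**The concern.** The covariate set is part of the primary analysis, and here it is settled only after by-arm data have been seen. SAP 1.1 says the plan should be detailed enough for someone else to run the analysis. On this item it is not: there is no candidate list, and what counts as imbalanced is left to the eye.

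The criterion is also the wrong one. The case for adjusting for a baseline variable in a randomised trial rests mainly on how strongly it predicts outcome. Under this rule a strong predictor that happens to look balanced is left out, and an irrelevant variable that happens to look imbalanced goes in.

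At stake are the odds ratio, risk difference and p-value for both co-primary outcomes in each arm comparison. SAP 4.1 tests these at 0.025, or at 0.05 for severe complications once the admission outcome is rejected, and calls the trial positive if either outcome succeeds. A p-value near a boundary could fall either side depending on which variables someone judged imbalanced.

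**Working it through.** **1. Is the gap closed elsewhere?** I compared the relevant sections.

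- SAP 6.2.2 and Protocol 8.3.1: stratification factors fixed; everything else by visual imbalance.
- SAP 6.2.4: sensitivity analyses vary the encounter set, the hospitalisation and referral definitions, and missing-data handling. None fixes or varies the covariates.
- SAP 6.2.5: age, sex and cough or difficulty breathing appear as effect modifiers, not as adjustment covariates.
- SAP 5.5: danger signs are summarised, not named for adjustment.

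Nothing closes it.

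**2. Does the planned size rely on covariates?** Inputs from SAP 3.4: 80% power, alpha 0.05 (taken as two-sided), ICC 0.001, severe complications 1.1% to 0.77%, appropriate hospitalisation 1.5% to 1.95%. A two-proportion calculation needs 13,351 and 13,141 children per arm before clustering.

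- Tanzania, 1,680 per cluster: design effect 1 + 1,679 × 0.001 = 2.679. Clusters per arm: 13,351 × 2.679 / 1,680 = 21.3, and 21.0 for the second outcome. The plan has 22.
- India, 510 per cluster: design effect 1 + 509 × 0.001 = 1.509. Clusters per arm: 39.5 and 38.9. The initial calculation has 40.

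The plan's figures reproduce with no covariate adjustment, so fixing a covariate list changes none of them.

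**3. How large would chance imbalances be?** The tables hold child-level and caregiver-level variables. For a child characteristic with 50% prevalence and 22 × 1,680 = 36,960 children per arm in Tanzania, the SE of the arm difference is √[2 × 0.25 / 36,960 × (1 + 1,679 × ICC)]. The documents give no ICC for baseline variables. I use the plan's outcome ICC and then assumed values:

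| ICC | SE (percentage points) |
|---|---|
| 0.001 | 0.6 |
| 0.01 (assumed) | 1.6 |
| 0.05 (assumed) | 3.4 |
| 0.10 (assumed) | 4.8 |

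Chance gaps range from negligible to several points, depending on how much the variable clusters by facility. With no threshold, analysts could reasonably disagree about gaps of a few points.

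**4. What does the rule do to the analysis?** An illustrative simulation used a cluster-level linear model under the null, with 22 or 60 clusters per arm and eight candidate covariates. Two of these were prognostic, together explaining 20% or 50% of between-cluster variance. The visible-imbalance cut-off was 0.1, 0.25 or 0.5 SD, with 4,000 runs per setting. All of this is assumed apart from the cluster counts.

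- At least one prognostic covariate was omitted in about 45% to 100% of runs.
- Between 13 and all 256 possible covariate sets were selected across runs.
- SD of the estimate, imbalance rule against the two prognostic covariates fixed: 0.25–0.30 against 0.22–0.28 (22 clusters); 0.14–0.18 against 0.13–0.17 (60 clusters).
- Type I error with the rule applied mechanically: about 2–5%.
- Type I error if the cut-off is picked after seeing p-values: about 8–12%.

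**5. Precision at the trial's event rate.** A separate logistic check ignored clustering. It used 73,920 children (2 × 36,960), an event rate of about 1%, and an assumed covariate with 10% prevalence and odds ratio 5. The SE of the treatment log odds ratio was 0.0713 unadjusted and 0.0716 adjusted, so one strong child-level predictor barely changes precision.

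**The case against.** The strongest reply is that little harm follows. The stratification factors are in every model. Avoiding significance tests of baseline balance is sound practice. Outcomes are also shown separately for infants under 60 days (SAP 6), and SAP 1.1 requires analyses outside the plan to be labelled and justified. Children are recruited after facilities are allocated, so imbalance may reflect differential recruitment, and a rule that responds to it is a reasonable safeguard. All of this is fair. It limits the size of the problem and argues for keeping imbalance-driven adjustment somewhere. It does not make the primary model reproducible.

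Three stronger readings are tempting, and the documents support none of them.

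- **Inflated type I error.** A reader might infer this from data-driven selection. Inflation in step 4 needed the choice to be informed by outcome results. The documents do not plan that, although they do not prevent it either.
- **Large imbalances are expected because there are only 22 facilities per arm.** One could compute √(2 × 0.25 / 22) = 0.151 and expect gaps of 15 points or more in about a third of randomisations. That describes a facility-level characteristic under unstratified randomisation. Randomisation was stratified, and the inspected variables are at child and caregiver level. Even at an ICC of 0.10, a 15-point gap has probability below 0.2% (15 / 4.8 is about 3.1 SEs).
- **Substantial lost power.** The precision loss in step 4 rests on assumed cluster-level covariates in a linear model. Step 5 suggests that child-level covariates would change little.

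**Conclusion.** The point holds in a limited form. Apart from the stratification factors, the covariates in both co-primary models are decided by looking at by-arm tables, with no list or threshold, and no planned analysis fixes them. The primary model is data-dependent and cannot be reproduced from the plan, and it adjusts on imbalance rather than prognosis.

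The size is moderate. The sample size is unaffected and type I error is not inflated by the rule as written. The precision at stake is probably modest with events near 1%, although that rests on an unclustered check with one assumed covariate. How far the odds ratio and p-value would move cannot be computed from the documents. The change is still worth making, because a better rule uses data already planned for collection and removes a choice that could later be questioned.

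**What to change.** In SAP 6.2.2, replace the visual-imbalance rule with a fixed covariate set for the primary models:

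- the randomisation factors as used in SAP 3.2: facility type and urban/rural location in Tanzania, facility type and district in India (6.2.2 says only location, so the India term needs naming);
- Day 0 age group, sex, and cough or difficulty breathing, as already defined in SAP 6.2.5.

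Two details need stating:

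- **Danger signs.** Include caregiver-reported danger signs only with a rule that keeps critical and emergency children in the model, for example a missing category. Protocol 6.5.1 exempts these children from pre-consultation data collection, so the item may be missing or recorded late for the sickest. A complete-case fit could then drop likely events.
- **Age.** Say how categories that straddle a cut are assigned. The 12–14 month category in SAP Appendix A crosses the boundary between the 2–12 and 13–59 month groups.

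Keep adjustment for visibly imbalanced variables as a labelled sensitivity analysis in SAP 6.2.4. Because Protocol 8.3.1 has the same rule, the SAP must declare the departure, as its section 1.1 allows.

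The cost is wording; no new data and no change in sample size are needed. The downside is that an imbalanced variable outside the list, including one arising from differential recruitment, is adjusted for only in the sensitivity analysis.

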6.2.3 Test of Assumptions, Actions to be taken

Continuous variables will be inspected using histograms: 1) to assess for outliers which may be queried for accuracy, and 2) to assess whether appropriate transformations are required for analyses.

As a multilevel logistic regression model is estimated using quadrature (rather likelihood methods), a quadrature check to test for adequate model fit will be performed. In case of unreliable model fit, generalised estimating equations will be used to fit the model which will provide population-averaged odds ratios and 95% confidence intervals.

6.2.4 Pre-planned Sensitivity Analyses

Sensitivity analyses on the primary outcomes are planned and will be conducted:

- ξ On first encounters, which will include only the first enrolment episode of each child during the study period (as some children may attend the facility on more than one occasion). Separate presentations are identifiable from Day0 form as the caregiver is asked whether the child attended previously and within 28 days. This is the minimum number of days required for the disease episode to be considered a new one and not a repeat visit.
- ξ Looking at different hospitalisation appropriateness (based on different definitions of primary and secondary hospitalisations). Same day (Day0), 3 days and 7 days from Day0 will be used as cut-offs for different primary and secondary hospitalisation definitions.
- ξ Looking at different referral definitions:
 - ο A child will be considered to be referred if, at Day0, caregiver confirms that the child was urgently referred *and* the research assistant confirms that an urgent referral advice was recorded for the child².
 - ο A child will be considered to be referred if, at Day0, the research assistant confirms that an urgent referral advice was recorded for the child. If urgency is unknown, referral will be assumed to be urgent.

Additionally, a set of sensitivity analyses on the primary outcomes shall be carried out in case of substantial missing data (e.g. >10%) to evaluate the impact of each method on the primary outcomes results and take them into account when interpreting the final analysis results. Planned methods will include:

- ξ Worst case scenario
- ξ Complete cases
- ξ Multiple imputations with chained equations [11, 12]

Details of the methods are provided in Section 6.3.

Sensitivity analyses will only be performed for the final statistical analysis and not for interim analyses and DMC reports.

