8.2.4 Data quality assurance and control

Quality assurance activities across all studies will be more intense during study start-up to ensure quality data practices are instituted from the start of the trial. Further details will be given in the DMP and SOPs.

All research assistants will be trained to provide information and seek written consent using the information and consent form. Separate trainings will cover all aspects of quantitative data collection and all aspects of qualitative data collection. A competency assessment using scenarios will be done before commencing field work.

Data reconciliation between the different visits of the same child will be one of the most crucial data quality activity in the pragmatic cluster RCT. Specific procedures will be developed for this purpose. To identify repeat visits of children that may re-attend the study facility where they enrolled or any other study facility during the follow-up period, participants will be given a study card (or sticker) with a unique ID number. Retrospective search for data at referral level will be restricted to facilities within the geographical area where the study is running and will be targeted to include only children reported to have attended hospital by the caregiver at follow-up and referred children lost to follow-up. The name of the referral facility will be requested during the follow-up call. If available, it should further restrict the scope of the search and the probability of negative matches when cross-checking the participant identity. Children who re-attend any study facility more than 28 days after their previous enrolment will be enrolled for the new disease episode and given a new ID number. If available, the old ID number will be recorded to facilitate linking of the different disease episodes. Data to be potentially reconciled will be flagged by automated cross-check of a set of personal identifiers. Given that

personal identifiers may not be identically recorded at each visit, fuzzy matching methods will be used to calculate a score of similarity between records and likelihood that they relate to the same child. Reconciliation of records with high similarity scores will be manually validated.

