If we fail to reject the null hypothesis H_{12} then we will stop and this point and conclude that the study is negative as neither of the co-primary outcomes were significant. If we reject the null hypothesis H_{12} then we would go on to test H_1 and H_2 . If $p_2 \leq \alpha_2$ then we reject H_2 and test H_1 as $p_1 \leq \alpha$. If $p_2 > \alpha_2$ then we do not reject H_2 and test H_1 as $p_1 \leq \alpha_1$.

All outcomes will be evaluated regardless of the outcome of the first evaluation. For each intervention arm, the overall trial will be interpreted as positive if either primary outcome is

positive compared to control. This will be assessed separately in India and Tanzania and will also be assessed across the two countries.

Missing data on key endpoints is to be expected due to the pragmatic nature of the study. If substantial data are missing (e.g. >10%), a set of sensitivity analyses shall be carried out where missing data are handled following different approaches such as, best/worst case scenario, complete cases, simple imputation or multiple imputation with chained equations (71, 72). The impact of each method on the primary outcomes results will be taken into account when interpreting the final analysis results. Further information on missing data handling will be detailed in the SAP.

We will conduct planned subgroup analysis of the primary outcomes to assess effect modifiers, specifically age, sex, clinical presentation (particularly cough / difficulty breathing) and diagnosis (particularly severity classification) and healthcare provider decision-making (particularly referral and antimicrobial prescription). Effect modification will be assessed by incorporating an interaction between trial arm and the variable in the model, acknowledging that power will be low. Planned sensitivity analysis will be conducted including only the first disease episode of each child during the study period (as some children may attend the facility on more than one occasion over the 12-month period). Further exploratory analysis will be detailed in the SAP.

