5.2 Eligibility

The following are inclusion and exclusion criteria that determine facility and child eligibility:

Facility inclusion:

- ξ Consenting government-designated healthcare facilities within the selected geographical areas of each country
- ξ Providing curative primary care services for children 0 – 59 months of age
- ξ Oxygen available or referral mechanism in place with oxygen available at a higher level facility
- ξ Electricity available (from any source with continuous or intermittent supply)

Facility exclusion:

- ξ Attending to fewer than 20 sick children per month (based on the prior 12 month average)
- ξ Already using pulse oximetry as a routine part of outpatient-based consultations of children 0 – 59 months
- ξ Selected to be part of a major child health programmatic or research intervention during the study period likely to significantly affect the primary outcome
- ξ Inaccessible to the study team (e.g. due to weather conditions or security issues) for significant parts of the year.

Individual child inclusion:

- ξ Children 0 – 59 months for whom caregivers provide consent
- ξ Consulting for an illness, or reported to be unwell when attending for a routine visit (e.g. vaccination, growth or chronic disease monitoring)

Individual child exclusion:

- ξ Children in the immediate post-natal period or first day of life
- ξ Attending for a consultation related to trauma only (including new and follow-up presentations for burns, injuries, wounds)
- ξ Admitted within an inpatient part of the facility (including neonates delivered at the facility admitted with their mother)
- ξ Enrolled in the study within the preceding 28 days at any study facility

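### The first-enrolment sensitivity analysis names only a caregiver's answer about earlier attendance, which cannot reliably separate first from later enrolments

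*SAP*

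**What the plan says.** **Target set.** SAP 6.2.4 describes a sensitivity analysis "which will include only the first enrolment episode of each child during the study period". Protocol 8.3.1 plans the same thing without a method: "Planned sensitivity analysis will be conducted including only the first disease episode of each child during the study period".

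**How the set is found.** The SAP's next sentence is the only one on method: "Separate presentations are identifiable from Day0 form as the caregiver is asked whether the child attended previously and within 28 days". It then explains the 28 days: "This is the minimum number of days required for the disease episode to be considered a new one and not a repeat visit".

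**Who can be enrolled again.** A child is excluded if "Enrolled in the study within the preceding 28 days at any study facility" (SAP 5.2, and likewise Protocol 6.2.1). Under Protocol 8.2.4, a child who comes back to any study facility after that interval is enrolled afresh under a different ID.

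**What linkage is planned.** Protocol 8.2.4 gives participants a card or sticker with a unique ID and adds: "If available, the old ID number will be recorded to facilitate linking of the different disease episodes". It also plans fuzzy matching on personal identifiers, with manual validation of high-scoring pairs. Protocol 8.2.1 uses the identification database to flag possible duplicates. SAP 6.2.4 mentions none of this.

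**The concern.** The target is a property of enrolment in this trial: is this the child's first record in the definitive dataset? The stated source is a report of attendance, with a 28-day element that serves to tell a repeat visit from a new episode. These are different questions.

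The primary model (SAP 6.2.1) has a random effect for the cluster and no term for the child, so several episodes of one child enter as separate records. The restriction to first enrolments is the only planned sensitivity analysis of that. The others in SAP 6.2.4 vary the hospitalisation and referral definitions or the handling of missing data. If the restricted set is built wrongly, agreement with the primary result may reassure falsely. A difference could come from a change in population rather than from removing repeats.

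**Working it through.** No figure in the plan describes repeat enrolment, so this is mainly a check of one text against another.

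**Step 1: the 28-day element.** By the exclusion, a correctly enrolled child has no enrolment in the preceding 28 days, whether this is the first or a later enrolment. Later enrolments arise only after that interval. An unenrolled visit in the last 28 days can precede either kind. The element therefore does not separate the two.

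**Step 2: the attendance element.** Attendance without enrolment in the definitive trial can arise in several ways:
- visits before the trial;
- visits in the pilot, whose data are set aside from the definitive analysis (Protocol 5.1);
- visits outside the working hours in which screening takes place (Protocol 10.3.1);
- visits where consent was refused (SAP 5.3).

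In the other direction, SAP 6.2.4 speaks of a child attending the facility, while exclusion and re-enrolment apply to any study facility. A caregiver answering about this facility only may not report an enrolment elsewhere.

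**Step 3: the most favourable reading.** Suppose the form has two separate items. Each answer pattern still contains both kinds of record:

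| Child's history at Day 0 | True status | Attended before | Within 28 days |
|---|---|---|---|
| Never attended | First | No | No |
| Enrolled over 28 days ago at another study facility, answer given for this one | Later | No | No |
| Attended before the trial only | First | Yes | No |
| Enrolled here over 28 days ago | Later | Yes | No |
| Seen in the last 28 days, not enrolled then | First | Yes | Yes |
| Enrolled over 28 days ago, seen again since without enrolment | Later | Yes | Yes |

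The answers carry some information, but no rule based on them recovers the target set.

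**Step 4: scale, on assumed shares only.** Planned sizes per arm (Protocol 6.6.1, SAP 3.4):
- Tanzania: 22 × 1680 = 36,960.
- India: 40 × 510 = 20,400. This is the initial calculation; the plan later allows up to 60 facilities per arm.

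Let *r* be the share of enrolments that are second or later, assumed 10–30%. Let *q* be the share of true first enrolments with earlier unenrolled attendance, assumed 10–50%. Neither is in the documents.

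- If only the 28-day answer is used and no later enrolment is caught, later enrolments kept = N × *r*. Tanzania: 36,960 × 0.10 = 3,696 to 36,960 × 0.30 = 11,088. India: 2,040 to 6,120.
- If any earlier attendance counts as a repeat, true first enrolments dropped = N × (1 − *r*) × *q*. Tanzania: 36,960 × 0.70 × 0.10 = 2,587 to 36,960 × 0.90 × 0.50 = 16,632. India: 20,400 × 0.70 × 0.10 = 1,428 to 20,400 × 0.90 × 0.50 = 9,180.

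These ranges show only that the result depends on a rule the SAP does not state and on shares nobody has reported.

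**Step 5: whether it can be repaired later.** Each episode gets a new ID. Under Protocol 8.2.1, the identification database stays in the country, the mapping between databases is not accessible outside the research institution, the core team receives de-identified copies, and the mapping database is eventually destroyed. An analyst who has not been given a child key or a first-enrolment flag may have only the Day 0 answer to work with.

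**The case against.** The best defence is that this is a missing cross-reference. The SAP states the target set correctly, does not say that the caregiver's answer is the sole selection rule, and declares itself in line with the protocol except where it says otherwise (SAP 1.1). The linkage in Protocol 8.2.4 would then still be available. The exact wording of the Day 0 form is not in the documents supplied. It may ask about enrolment at any study facility, with attendance as the SAP's shorthand.

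Much of this stands. A reader might infer that the answer carries no information at all. That would hold if the form has a single question about the last 28 days, but a two-part question does carry some. A reader might also infer that the SAP has rejected linkage; it has only left it out. And a reader might assume that a persistent child ID already exists. It does not: the old ID is recorded only if available, and the rest depends on similarity scores.

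It is also fair to say that re-enrolment is deliberate and that the 28-day exclusion, correctly applied, keeps the Day 7 outcome windows of one child's episodes apart.

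The defence does not remove the problem. Someone who follows SAP 6.2.4 as written would build the set from the caregiver's answer, because it names no other source, and would misclassify children.

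**Conclusion.** The point holds in a limited form. The method named in SAP 6.2.4 cannot reliably identify each child's first enrolment, and a better source already planned in the protocol is not used. The size of the misclassification is unknown, and the ranges above rest entirely on assumed shares.

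The effect is confined to one sensitivity analysis. The primary analysis set, its estimates and the testing procedure are unaffected, so the documents do not support an inference that the main result is compromised. Nor do they support saying that the analysis must remove either almost no one or the wrong children, that the children left would be younger, or that a particular fraction of each arm would be lost. The analysis still deserves correction, because no other planned sensitivity analysis addresses one child contributing several episodes.

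**What to change.** Replace the identification sentence in SAP 6.2.4 with a rule such as:

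> The first enrolment is the earliest Day 0 date in the definitive trial for each linked child, across all study facilities. Children are linked by the recorded old ID and by manually validated identifier matches (Protocol 8.2.4). The caregiver's Day 0 answer is used only as a cross-check.

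Also specify that:
- the country data managers supply a de-identified child key or first-enrolment flag with the analysis dataset, before the mapping database is destroyed;
- the number of repeat enrolments and the share of records with uncertain linkage are reported by arm.

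The cost is a change of SAP wording and one extra variable from data management, since the matching is already planned. The drawback is that linkage may be incomplete: a missed match keeps a later enrolment in the set, and a false match removes a true first one. Reporting uncertain links by arm lets readers judge this.
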